10.2.6.7 Treatment Dose Modifications and Guidelines for Diarrhea

Etiology and attribution:

Consider evaluation for an alternative etiology of diarrhea as clinically indicated. These include medications (e.g., stool softeners, laxatives, antacids, etc.), infection by *C. difficile*,

partial bowel obstruction, malabsorption/lactose intolerance, fecal impaction, or diets high in fiber or lactose.

For Grade ≤ 2 diarrhea:

Dietary modifications may include stop all lactose-containing products and eat small meals. A banana, rice, apples, toast (BRAT) diet can be helpful. Encourage oral hydration according to institutional weight oral hydration guidelines as clinically appropriate.

For all subjects consider administration of loperamide with dosing per institutional guidelines or as suggested below. Continuation of loperamide is suggested until the subject is diarrhea-free for at least 12 hours.

Suggested Loperamide Dosing				
Age	Weight (kg)	Initial Dose (after first loose bowel movement)	Subsequent doses	Maximum daily dose
> 1 mo to ≤ 12 years	< 13	0.5 mg	0.5 mg every 3 hr while awake, every 4 hr during sleep	4 mg/day
	13 to < 20	1 mg	mg every 4 hr	6 mg/day
	20 to < 30	2 mg	1 mg every 3 hr while awake, every 4 hr during sleep	8 mg/day
	30 to < 43	2 mg	1 mg every 2 hr while awake, every 4 hr during sleep	12 mg/day
≥ 13 years	>43	4 mg	2 mg every 2 hr while awake, every 4 hr during sleep	16 mg/day

- If diarrhea resolves to Grade ≤ 1 or baseline within 72 hours of anti-diarrheal measures or supportive care measures, continue study treatment without interruption or dose reduction.
- If Grade 2 diarrhea persists after 72 hours total treatment with loperamide or supportive measures in children < 2 years, hold study treatment and consider start of second-line agents (octreotide) as clinically indicated.
- If diarrhea resolves to Grade ≤ 1 or baseline >72 hours but within 7 days then may resume study treatment with a dose reduction as per [Section 10.2.3](#).
- If Grade 2 diarrhea does not resolve to Grade ≤ 1 or baseline in ≤ 7 days without study treatment, discontinue protocol therapy.

For Grade 3 diarrhea:

- If loperamide has not been initiated, initiate loperamide immediately using institutional or protocol guidelines for dosing as above. For dehydration, use intravenous fluids as appropriate; if severe dehydration, consider administration of octreotide.
- Hold study treatment until symptoms resolve to \leq Grade 1 or baseline.
 - If diarrhea resolves to Grade \leq 1 or baseline within 72 hours of anti-diarrheal measures or supportive care measures, may resume study treatment without dose reduction as per [Section 10.2.3](#). If diarrhea Grade \geq 3 recurs subject is not eligible for resumption of treatment without dose reduction.
 - If diarrhea resolves to Grade \leq 1 or baseline >72 hours but within 7 days, then may resume study treatment with a dose reduction as per [Section 10.2.3](#).
 - If diarrhea does not resolve to Grade \leq 1 or baseline in \leq 7 days without study treatment, discontinue protocol therapy.

For Grade 4 diarrhea:

- If loperamide has not been initiated, initiate loperamide immediately using institutional or protocol guidelines for dosing as above. For dehydration, use intravenous fluids as appropriate; if severe dehydration, consider administration of octreotide.
- Hold study treatment until symptoms resolve to \leq Grade 1 or baseline.
 - If diarrhea resolves to Grade \leq 1 or baseline \leq 7 days without study treatment, then may resume study treatment with a dose reduction as per [Section 10.2.3](#).
 - If diarrhea does not resolve to Grade \leq 1 or baseline in \leq 7 days without study treatment, discontinue protocol therapy.

10.2.6.8 Treatment Dose Modifications and Guidelines for Visual Disturbances

Trametinib is known to be associated with visual adverse events. An age-appropriate comprehensive ophthalmologic examination should be performed by an ophthalmologist (without sedation) at screening, including a dilated funduscopy evaluation to rule out retinal vein occlusion (RVO) and retinal pigment epithelial detachment (RPED). During the study, ophthalmologic exams will be repeated by an ophthalmologist per Study Assessments [Section 8.1](#). These exams will be directed by the subject's complaints but will still include best corrected visual acuity, evaluation of the anterior segment, and direct or indirect ophthalmoscopy. A dilated eye exam is encouraged, but not required at each follow-up visit. Optical coherence tomography (OCT) will not be performed during these exams unless the child has a symptom or exam finding that the physician believes warrants this type of imaging. As is the standard of care for any subject on a MEK inhibitor the development any visual complaint will necessitate immediate evaluation and Ophthalmology should be consulted.

Management and Trametinib Dose Modifications for Visual Changes and/or Ophthalmic Examination Findings		
Event CTCAE Grade (NCI v5.0)	Recommended Management Guidelines	Dose Modification Requirement

Grade 1: Asymptomatic; clinical or diagnostic observations only.
 
Note: if visual changes are clearly unrelated to study treatment (i.e.allergic conjunctivitis), monitor closely but ophthalmologic exam not required
	
Initiate local therapy and consult ophthalmologist within 7 days of onset
	
If dilated fundoscopic examination cannot be performed within 7 days of onset, hold treatment until RPED and RVO can be excluded by ophthalmologist.
 
If RPED and RVO excluded, continue (or restart) treatment at same dose.
 
 ▪ If RPED suspected/diagnosed: see RPED dose modification table below (following this table); report as SAE ▪ If RVO diagnosed: permanently discontinue treatment and report as SAE.

Grade 2 and Grade 3:
 
Symptomatic with mild to moderate decrease in visual acuity; limiting instrumental ADL
	
Consult ophthalmologist immediately
	
For RPED and RVO:
 
 ▪ Hold treatment. ▪ If RPED and RVO excluded: restart treatment at same dose level. ▪ If RPED diagnosed: see RPED dose modification table below (following this table); report as SAE. ▪ If RVO diagnosed: permanently discontinue treatment and report as SAE. 
For uveitis:
 
 ▪ Hold treatment.

Grade 4:
 
Sight threatening consequences; urgent intervention indicated; best corrected visual acuity of 20/200 or worse in the affected eye
	
Consult ophthalmologist immediately
	
Interrupt treatment.
 
 ▪ If RPED and RVO excluded: consider restarting treatment at the same or reduced dose level, after discussion with study chair. ▪ If RVO or RPED diagnosed: permanently discontinue treatment and report as SAE.

Mandatory dose modification and recommended clinical management for retinal pigment epithelial detachments (RPED suspected to be related to trametinib treatment)

Retinal Detachment (NCI CTCAE v5.0)	Recommended Management Guidelines	Dose Modification Requirement
Grade 1–2: (Asymptomatic; clinical or diagnostic observations only)	Retinal evaluation monthly.	
 Continue treatment with retinal evaluation monthly until resolution. If RPED worsens, follow instructions below.
Grade 3–4: (Symptomatic with mild to moderate decrease in visual acuity; limiting instrumental ADL)	Retinal evaluation monthly.	
 Hold treatment. If improved to \leq Grade 1, restart treatment at reduced dose (to the next lower dose according to Appendix II). If no recovery within 4 weeks permanently discontinue trametinib treatment

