10.2.3 Dose Modifications for Non-Hematologic Toxicity

If a subject experiences a dose-modifying non-hematologic toxicity as defined in [Section 10.2.1](#), the treatment will be held.

If the toxicity does not resolve to meet inclusion/exclusion parameters or baseline within 14 days of drug discontinuation the subject must be removed from protocol therapy unless specifically documented in toxicities of special interest [Section 10.2.6](#).

If the toxicity resolves to meet inclusion/exclusion parameters or baseline within 14 days of drug discontinuation the subject may resume treatment with a reduction to the next lower dose according to [Appendix II](#). See [Appendix II](#) for dosing modification in subjects receiving oral solution or the specified dose reduction in subjects receiving tablets.

- Doses reduced for toxicity will not be re-escalated, even if there is minimal or no toxicity with the reduced dose, unless otherwise specified in the toxicities of special interest [Section 10.2.6](#).
- If the same dose-modifying toxicity recurs in a subject who has resumed treatment, the subject must be removed from protocol therapy.

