condition, other concomitant events). Although an adverse drug event may rate only as “possibly related” soon after discovery, it can be flagged as requiring more information and later be upgraded to “probably related” or “definitely related”, as appropriate.

Unlikely: A clinical event, including an abnormal laboratory test result, whose temporal relationship to drug administration makes a causal relationship improbable (e.g., the event did not occur within a reasonable time after administration of the trial medication) and in which other drugs or chemicals or underlying disease provides plausible explanations (e.g., the subject’s clinical condition, other concomitant treatments).

Unrelated: The AE is completely independent of study drug administration, and/or evidence exists that the event is definitely related to another etiology. There must be an alternative, definitive etiology documented by the clinician.

10.10 Treatment Dose Modifications and Guidelines for Adverse Event Reporting specific to study drug

Dose modifying hematological and non-hematological toxicities are defined differently. Dose modification or discontinuation of trametinib for toxicity is considered a dose modifying toxicity. Guidelines for management and dose modifications are also provided for the toxicities of special interest.

Trametinib Dose Modification Schedule for Adverse Events

Grade (CTC-AE)*	Schedule
	Grade (CTC-AE)* Dose Modifications
Grade 1 or Grade 2 (Tolerable)	Continue treatment and monitor as clinically indicated.
Grade 2 (Intolerable) or Grade 3	Interrupt therapy until toxicity is grade 0-1 and reduce by one dose level when resuming therapy.
Grade 4	Discontinue permanently, or interrupt therapy until Grade 0 to 1 and Reduce by one dose level when resuming therapy.

* The intensity of clinical adverse events graded by the Common Terminology Criteria for Adverse Events v4.0 (CTC-AE)

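### For Grade 3 and Grade 4 visual events with RPED and RVO excluded, Sections 10.2.6.8 and 10.10 give conflicting restart instructions, and neither is said to govern

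*Protocol*

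**What the plan says.** Protocol Section 10.2.6.8 contains a table for visual changes, with a column of required dose modifications.

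- **Grade 2 and Grade 3.** One block of the cell is headed "For RPED and RVO". It holds treatment and then says "If RPED and RVO excluded: restart treatment at same dose level". A second block, headed for uveitis, contains only an instruction to hold.
- **Grade 4.** Treatment is interrupted, and then: "If RPED and RVO excluded: consider restarting treatment at the same or reduced dose level, after discussion with study chair".

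Section 10.10 has a schedule of dose modification by grade for adverse events in general.

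- **Intolerable Grade 2, or Grade 3.** "Interrupt therapy until toxicity is grade 0-1 and reduce by one dose level when resuming therapy".
- **Grade 4.** Either a permanent stop, or interruption until Grade 0 to 1 followed by a one-level reduction.

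Section 10.10 mentions that guidance for toxicities of special interest is provided as well. It does not say which applies when the two differ.

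Section 10.2.3, the general rule for non-hematologic toxicity, says: "If the toxicity resolves to meet inclusion/exclusion parameters or baseline within 14 days of drug discontinuation the subject may resume treatment with a reduction". Visual disturbances are on the special-interest list in Section 10.2.6.

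**The concern.** A site managing a Grade 3 visual event has ruled out RPED and RVO. Under Section 10.2.6.8 the drug restarts at the same dose, whether or not vision has recovered. Under Section 10.10 the drug stays off until the event is Grade 0-1 and then restarts one level lower. For Grade 4, one section leaves same-dose restart open and the other does not.

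This decides whether a subject with unresolved visual loss is re-exposed, and at what dose the subject reaches the cycle 6 assessment. It also bears on recurrence: Section 10.2.3 removes a subject if the same dose-modifying toxicity recurs after treatment resumes, while the visual-changes table has no recurrence rule.

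The point concerns only events in which RPED and RVO have been excluded, not the handling of diagnosed RPED.

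**Working it through.** The conflict does not depend on any design figure, so the check is a comparison of the texts, followed by a rough count of the subjects affected.

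**Step 1. Restart rules side by side, RPED and RVO excluded**

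| Event | Section 10.2.6.8 | Section 10.10 | Same instruction? |
|---|---|---|---|
| Grade 3, recovery needed | none stated | Grade 0-1 | No |
| Grade 3, dose on restart | same level | one level lower | No |
| Grade 4, recovery needed | none stated | Grade 0-1, if not stopped permanently | No |
| Grade 4, dose on restart | same or reduced, after study chair discussion | one level lower, if not stopped permanently | Only if the reduced option is taken |

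An intolerable Grade 2 event falls in the same rows as Grade 3 in both sections, so it meets the same conflict. Grade 1 does not: both sections let treatment continue once RPED and RVO are excluded.

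**Step 2. Does Section 10.10 yield?** Its schedule exempts no event. Its reference to special-interest guidance only says that such guidance exists.

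**Step 3. Does Section 10.2.3 conflict too?** Under Section 10.2.1.1, Grade 3 and Grade 4 non-hematological toxicities are dose-modifying, and visual events are not among the listed exceptions. Section 10.2.3 then requires resolution within 14 days and restart at the next lower dose. It defers to Section 10.2.6 in two places: the removal sentence, with the words "unless specifically documented in toxicities of special interest", and the bullet on re-escalation. The sentence that imposes the reduction has no such clause. However, Section 10.2.1.1 sends special-interest toxicities to Section 10.2.6 for management, so this is a partial conflict.

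**Step 4. Is the missing recovery condition usual for Section 10.2.6?** No. The subsections on rash, CPK, LVEF, pneumonitis, diarrhea and hypertension, and the separate RPED table, each state a recovery condition for restarting after a hold. The branch with RPED and RVO excluded does not.

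**Step 5. Uveitis.** Its only instruction is to hold. No restart criterion, time limit or stopping rule follows.

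**Step 6. How many subjects.** Inputs are from Section 1.2.2 (adults at 2 mg daily): visual disorders in 14% to 18%; of these, 7% to 29% Grade 3 and none Grade 4. The planned number is 39 evaluable subjects (Section 9.1).

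- Any visual disorder: 39 × 0.14 = 5.46 to 39 × 0.18 = 7.02.
- Grade 3: 5.46 × 0.07 = 0.38 to 7.02 × 0.29 = 2.04, so about 0.4 to 2 subjects.

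This count is taken before removing cases with RPED or RVO and cases unrelated to the drug.

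**The case against.** The strongest reply is that a specific rule displaces a general one. Section 10.2.1.1 points to Section 10.2.6, and other subsections plainly depart from the general rule: Grade 3 diarrhea that resolves within 72 hours may resume without a reduction, and an asymptomatic Grade 3 CPK elevation keeps its dose. On that reading the visual-changes table simply governs.

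Much of this stands against the conflict with Section 10.2.3, and a reader who infers a flat contradiction there goes too far. It does not settle the conflict with Section 10.10, which contains no deference. Nor does it explain the silence on recovery: the diarrhea exception asks for resolution first, and the visual branch does not.

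A second reply is scope. Section 10.2.1 limits dose-modifying toxicity to events at least possibly attributable to trametinib, while the Grade 2 to 4 visual rows state no attribution condition. Part of the difference from Section 10.2.3 may therefore be scope. For an attributable Grade 3 or 4 event the rules still overlap.

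Third, the Grade 4 row is not a plain permission to restart. It says "consider restarting treatment at the same or reduced dose level, after discussion with study chair", so a reduced dose and a consultation are both available. That softens the Grade 4 conflict on dose but leaves the recovery condition unaddressed.

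A reader might also infer that the Grade 2-3 cell tells a site both to hold and to restart a uveitis case. The layout does not support this, because the restart bullet sits under a different heading. The cell could be misread that way, but the defect is a hold without an end.

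**Conclusion.** The protocol gives different restart conditions and doses for the same Grade 3 or Grade 4 visual event when RPED and RVO are excluded, and does not say which section prevails. The conflict is clear between Sections 10.2.6.8 and 10.10, and weaker between Sections 10.2.6.8 and 10.2.3. The uveitis hold is separately incomplete.

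Few subjects would be affected: about 0.4 to 2 of 39 with a Grade 3 visual disorder, if adult rates carry over to this mostly younger population, and no Grade 4 case can be projected from those data. Any effect on the cycle 6 response rate would be marginal. The reason to act is consistent handling of re-exposure after visual loss.

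A reader might infer from the low rates of central serous retinopathy (1.2%) and RVO (0.3%) in Section 1.2.2 that nearly all visual disorders fall in the conflicting branch. The documents do not support that. Those rates and the 14% to 18% come from different denominators, Section 1.2.2 lists central serous retinopathy separately from RPED and gives no RPED rate, and 71% to 93% of the visual disorders were Grade 1 or 2, while the conflict lies mainly at Grade 3 and above.

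**What to change.** Reconcile the visual-changes table in Section 10.2.6.8 with Sections 10.10 and 10.2.3:

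1. For each grade with RPED and RVO excluded, give one restart condition, including whether recovery is required and to what grade, and one dose instruction.
2. State in Sections 10.2.3 and 10.10 whether the special-interest subsections override the general rules, and on which points: recovery, dose and recurrence.
3. State how the uveitis hold ends, preferably in a row of its own.

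The clinical content of each rule is for the sponsor to decide. The cost is a wording amendment; the sample size, schedule of assessments and analysis do not change.

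### Section 10.2.6.8 ends treatment for a Grade 4 RPED in one table, while the next table's restart row is labelled Grade 3–4 and so allows a reduced-dose restart after recovery

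*Protocol*

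**What the plan says.** Protocol section 10.2.6.8 handles eye toxicity in two consecutive tables. Both place their actions in a column of dose-modification requirements.

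The visual-changes table comes first. Its Grade 4 row is defined as "Sight threatening consequences; urgent intervention indicated; best corrected visual acuity of 20/200 or worse in the affected eye". If RPED or retinal vein occlusion (RVO) is found, the action is "If RVO or RPED diagnosed: permanently discontinue treatment and report as SAE". Re-treatment is contemplated only in the other branch: "If RPED and RVO excluded: consider restarting treatment at the same or reduced dose level, after discussion with study chair". The lower rows work differently. The combined Grade 2 and 3 row holds treatment and then says "If RPED diagnosed: see RPED dose modification table below (following this table); report as SAE", and the Grade 1 row makes the same referral.

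The RPED table comes second, headed "Mandatory dose modification and recommended clinical management for retinal pigment epithelial detachments" and limited to RPED suspected to be related to trametinib. Its Grade 1–2 row says "Continue treatment with retinal evaluation monthly until resolution" and then "If RPED worsens, follow instructions below". The only row below is labelled Grade 3–4. That row holds treatment and, on improvement to Grade 1 or less, directs sites to "restart treatment at reduced dose". It ends treatment permanently if there is no recovery within 4 weeks.

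**The concern.** A site managing a Grade 4 RPED that has recovered can find two different instructions in one section: no further trametinib, or trametinib at the next lower dose. The restart instruction does not require a discussion with the study chair, although the visual-changes table requires one before restart even when RPED and RVO have been ruled out.

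What is at stake is re-exposure after a sight-threatening toxicity, in a population that starts at 2 months of age and is spread over 25 sites. Two sites could treat the same clinical state differently and each point to protocol text in support.

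**Working it through.** There is no figure to reproduce; the check is a comparison of text.

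**1. The two instructions for a trametinib-related Grade 4 RPED**

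| Course of the event | Visual-changes table, Grade 4 row | RPED table, Grade 3–4 row |
|---|---|---|
| At diagnosis | Permanent discontinuation, SAE report | Hold |
| Improves to Grade 1 or less within 4 weeks | Remains discontinued | Restart at the next lower dose |
| No recovery within 4 weeks | Remains discontinued | Permanent discontinuation |

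The end states differ only in the middle line, so the conflict is confined to a Grade 4 RPED that recovers within 4 weeks.

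**2. How a subject reaches each row**

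- *First presentation at Grade 4.* The visual-changes table sends RPED onward at Grade 1 and at Grades 2 and 3, but not at Grade 4. Read in order, this subject stops at permanent discontinuation.
- *Already on the RPED table at Grade 1–2, then worsening to Grade 4.* The instruction is "If RPED worsens, follow instructions below", and the only row below permits restart. The same clinical state now carries a different rule because of the route by which it was reached.

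**3. Does the restart row really cover Grade 4?** By label, yes. By description, no: its descriptor is symptomatic, mild-to-moderate visual loss, the same description that the visual-changes table gives to Grades 2 and 3. Nothing in it corresponds to sight-threatening disease or acuity of 20/200 or worse. Label and descriptor disagree within the row.

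**4. Does another section decide?**

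- Section 10.2.3 requires removal if a dose-modifying toxicity has not resolved in 14 days, except where section 10.2.6 provides otherwise. That places 10.2.6 above the general rule but does not rank two tables inside 10.2.6.8.
- Section 10.10 accepts either permanent discontinuation or a reduced-dose restart after a Grade 4 event.

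Neither settles the matter.

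**5. Effect on the statistics.** Section 9.2 counts Grade 3–4 retinal detachment in the first two courses as a severe toxicity. The count depends on the event and its grade, not on the dosing action that follows. The stopping boundary, the sample size and the power are therefore unchanged under either reading.

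**6. Frequency.** The protocol gives no RPED rate. Section 1.2.2 reports no Grade 4 visual disorder in the three adult trials it describes at 2 mg daily. Any expected count for this trial would rest on an invented rate, so none is offered.

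**The case against.** The best defence is that the section already settles Grade 4. The visual-changes table is the point of entry, its referrals stop at Grade 3, and its Grade 4 row is complete in itself. The restart row describes milder disease, so the 4 in its label looks like a slip. A worsened eye at 20/200 is also a Grade 4 finding under the visual-changes table, and the section requires immediate ophthalmology evaluation of any visual complaint. The two tables also grade under different headings, one for visual changes or examination findings and one for retinal detachment, so a Grade 4 in one need not be a Grade 4 in the other.

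Much of this stands. It makes permanent discontinuation the likely intent and narrows the problem. It does not remove it: the RPED table is headed mandatory, names Grade 4, and is the table that a worsening subject is told to follow. If discontinuation is intended, the label is wrong.

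Three stronger readings might be inferred, and the protocol does not support them:

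- *That every Grade 4 RPED is sent to both tables.* It is not; the Grade 4 row of the visual-changes table makes no such referral.
- *That the tables also conflict at Grades 2 and 3.* They do not; the visual-changes table holds treatment and defers to the RPED table. There is only a small mismatch inside the RPED table, where a symptomatic Grade 2 RPED continues by grade number but is held by description.
- *That dosing could continue through active Grade 4 disease.* Neither table allows this; restart requires improvement to Grade 1 or less.

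**Conclusion.** The point holds as a labelling and routing error. A trametinib-related Grade 4 RPED that recovers to Grade 1 or less within 4 weeks may be restarted at a reduced dose under the RPED table and may not be under the visual-changes table, and the protocol does not say which governs. The clearest route into the conflict is an RPED that worsens while already being managed under the RPED table.

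This is a subject-safety wording matter. It should be rare, and its frequency cannot be estimated from the protocol. It does not touch the primary endpoint, the error rates or safety monitoring. It is worth correcting because the consequence for a subject could be serious and the correction is small. The conclusion that discontinuation is intended is an inference from the referral pattern and the row descriptor; the clinical team should confirm it.

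**What to change.** In the RPED table of section 10.2.6.8:

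1. Relabel the hold-and-restart row so that it excludes Grade 4.
2. Add a Grade 4 row, defined as in the visual-changes table (sight threatening, 20/200 or worse): discontinue permanently and report as an SAE.
3. Amend the worsening instruction in the Grade 1–2 row so that any RPED reaching Grade 4 goes to the new row.
4. If the Grade 2 mismatch is tidied at the same time, state that symptomatic RPED *below Grade 4* follows the hold row. The limit matters: a sentence covering symptomatic RPED of any grade would bring Grade 4 back under the restart rule.

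The cost is amendment wording in one table: one row split in two, one routing sentence changed and, optionally, one sentence added. No change to the design, the analysis or the section 9.2 event definition is needed.
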